The Impact of Carnosine Loading and Rehabilitation Therapy on Exercise Capacity in Multiple Sclerosis

NCT03418376

Date: 10/02/2017

PROTOCOL: IMPACT OF CARNOSINE LOADING ON HOME-BASED EXERCISE THERAPY EFFECTS IN MULTIPLE SCLEROSIS

INTRODUCTION

Multiple Sclerosis (MS) is a neurodegenerative inflammatory disease of the central nervous system¹ that is characterized by central nervous system demyelination and axonal loss causing a variety of symptoms such as spasticity, tremor, paralysis, walking difficulties and cognitive abnormalities². **Decreased exercise capacity, excessive (post-exercise) fatigue and reduced muscle contractile function^{3, 4} are frequently occurring comorbidities that substantially affect various daily life activities** leading to an inactive lifestyle and lower quality of life⁵. This results in a disuse-related physiological profile and thus even greater muscle weakness and health risks than provided by the disease *per se*⁶. In fact, in other populations muscle weakness is an independent predictor of premature death⁷. Central mechanisms contributing to the latter symptoms include reduced motor firing rates, impaired motor unit recruitment and increased central motor conduction time⁸⁻¹². However, **a portion of the neuromuscular dysfunction present in MS appears to reside within the affected muscle^{8-10, 12-15}**.

Exercise therapy and skeletal muscle dysfunction in MS

So far, recent immune-modulatory therapies decrease MS relapse rate and disease severity¹⁶ but they do not slow the disease process. Because such therapies, unfortunately, do not affect accumulation of MS disabilities and comorbidities and because at least some MS related impairments are inactivity related rather than a result of non-reversible tissue injury, exercise rehabilitation therapy has become an important part of overall MS treatment. Indeed, a multitude of low to moderate intensity **exercise intervention studies in MS** already reported small (+10-15%) but significant improvements in muscle strength and exercise capacity³. Surprisingly however, **effects are lower compared to healthy controls and some other disease populations**. In an attempt to further improve rehabilitation outcome we therefore recently performed higher intensity training (HIT) studies in an animal MS model (Experimental Autoimmune Encephalomyelitis, EAE¹⁷) and in MS patients¹⁸. Although results are promising with substantially improved (+25-30%) muscle strength and exercise capacity following 8-12w of exercise^{17, 18} most MS subjects reported **higher post exercise muscle fatigue and overall perceived exertion rates (BORG: 14.7±1.5 vs. 12.7±1.3)** compared to low-to-moderate intensity training¹⁵.

To date it is difficult to address the **underlying mechanisms of the overall therapeutic effect of exercise therapy in MS**. So far several **immune-related mechanisms** such as altered circulating cytokine levels and BDNF expression^{19, 20} following an acute exercise bout and longer term exercise have been described. We recently demonstrated reduced innate markers of inflammation²¹ and a rapid exercise-induced mobilization of dendritic cells that is possibly mediated by a Flt3L- and MMP-9-dependent processes²² following exercise in MS. This may indicate a negative feedback mechanism for the immune system's ability to induce tissue damage and inflammation following exercise. The above described neuro-immune mechanisms unfortunately remain largely **speculative** supporting the above mentioned hypothesis that indeed **part of the neuromuscular dysfunction could be situated in the affected muscle**. In this respect, we and others, have reported **altered muscle contractile characteristics** and muscle fibre composition (shift to glycolytic fibre types) as well as cross-bridge (Ca²⁺ handling) abnormalities in MS^{8, 14, 15}. Furthermore, **abnormal muscle energy metabolism in MS** has been demonstrated involving reduced Krebs cycle and complex I and II activities^{12, 23}, overproduction of reactive oxygen species (ROS²⁴), increased basal AMP-activated protein kinase phosphorylation²⁵ and delayed phosphocreatine resynthesis after exercise^{12, 13, 23, 25, 26}. This suggests higher basal and exercise related energy expenditure and increased exercise-induced intramyocellular lactate accumulation, and thus greater perceived muscle fatigue, as recently evidenced by increased basal²⁷ and exercise-induced (see Figure 1, [name] & [name] et al. *Manuscript in preparation*) serum

lactate concentrations. Thus, **impairments in both (I) muscle contraction and (II) energy supply seem to attenuate adequate exercise therapy outcome in MS**. Consequently, any strategy that improves muscle contraction and/or intramyocellular energy homeostasis during exercise training may therefore be an interesting tool to investigate the underlying mechanisms of the overall therapeutic effect of exercise therapy in MS and, as such, may help to further optimize exercise rehabilitation protocols.

[figure not shown]

Figure 1. Serum lactate concentrations (means \pm SE's) during submaximal (two 6-min exercise bouts [25% of W_{max}]) and maximal graded exercise testing (cycling) in healthy controls (HC, $n=17$) and multiple sclerosis (MS, $n=20$) patients (Pilot data taken from [name] & [name] et al. Increased exercise-induced lactate accumulation in MS. Manuscript in preparation).

Muscle carnosine loading

Carnosine (β -alanyl-L-histidine) is found in high concentrations in mammalian skeletal muscle^{28, 29}. Its **physiological role** is related to **(I) contractile function** in general and more specific to Ca^{++} handling²⁹. In addition, **(II)** carnosine has also been shown to **buffer muscle pH** resulting from exercise-induced acidosis²⁹ and it has been suggested to **affect mitochondrial respiration**³⁰ and to **protect against exercise-induced oxidative stress**³¹. Here, carnosine reduces the production of thiobarbituric acid reactive substances and malondialdehyde due to lipid peroxidation^{28, 29}. **High (or elevated) muscle carnosine content may thus be advantageous to improve muscle contractile properties and/or myocellular energy supply during exercise intervention.** Because skeletal muscle carnosine synthesis is mainly determined by β -alanine availability³², exogenous (dietary, 2-6g/d, 4-10w) intake of β -alanine has been successfully applied to increase muscle carnosine content (+80%, **carnosine loading**) in various rodent disease models³³⁻³⁵ and healthy volunteers³⁶⁻³⁸. In untrained and aged subjects β -alanine supplementation has recently been shown to specifically improve maximal power output (+13-30%) in exercise types lasting 1-4min³⁹. Interestingly, trained muscles load more efficiently with carnosine than untrained muscles⁴⁰. Consequently, β -alanine is rapidly becoming a popular **ergogenic substance** in the (clinical) exercise/sports community.

Carnosine's **therapeutic effect** has already been shown in Alzheimer's⁴¹ and Parkinson's²⁸ disease. In these neurological disorders **carnosine treatment** (~1.5g/d β -alanine) improved a number of neurological symptoms⁴². Interestingly, recent **pilot data (Figure 2) from the laboratories suggested substantially reduced (~60%) skeletal muscle carnosine content in EAE rats. In MS patients m. vastus lateralis carnosine content was reduced by ~20%**. Though, 12 weeks of (high intense) exercise training did not remediate this (PRE-POST $p>0.05$, Figure 2). Hence, carnosine treatment in MS could be a valid **new approach to further (I) improve exercise rehabilitation therapy in MS and (II) investigate the effects of MS on skeletal muscle**. The carnosine loading potential of β -alanine supplementation in EAE and MS patients, as well as its associated (therapeutic) effects on muscle contractile functioning and cellular respiration, however, have not been investigated thoroughly yet. In this regard, we have recently explored the effect of β -alanine and carnosine supplementation on muscle carnosine content during EAE. Here, β -alanine and carnosine intake delayed paralysis onset and peak as well as improved recovery. Furthermore (Figure 3) and compared to controls muscle carnosine concentrations substantially increased in these animals (Figure 4). These findings in an animal MS model warrant further exploration of the effects of muscle carnosine loading in MS.

[figure not shown]

Figure 2. Muscle carnosine concentrations (mmol/kg ww, means \pm SE's) in sedentary (SED, n=15) and exercised (EX, n=16) EAE rats (animal MS model), in healthy controls (HC, n=18) and in MS patients (n=16) before (PRE) and after (POST) 12w of exercise intervention. Muscle biopsies for this pilot study were provided by prof. dr. [name] (Hasselt University) and analysed by prof. dr. [name] (Ghent University). As these pilot data are believed to be pre-competitive, the data have not been published yet.

[figure not shown]

Figure 3. Clinical disease scores of EAE rats (animal MS model), without (control, n=13), with carnosine (carnosine, n=13) or β -alanine (β -alanine, n=13) supplementation. CID, Cummulative Disease Index. * p<0.05 for carnosine compared to control. ^ap<0.05 for carnosine compared to β -alanine.

[figure not shown]

Figure 4. Muscle carnosine concentrations (mmol/kg WW) in EAE rats (animal MS model), without (EAE CON, n=13) and with carnosine (EAE CA, n=13) or β -alanine (EAE BA, n=13) supplementation. *p<0.05 compared to control group.

Research objectives

Increasing evidence favours exercise therapy as an efficient tool to counteract inactivity related secondary symptoms in MS. Furthermore, exercise therapy may affect MS-associated muscle contractile and energy supply dysfunctions. So far, low to moderate intensity exercise rehabilitation has shown to induce small but consistent improvements in several functional parameters. High intensity exercise training in MS seems to further improve this. However, although results are promising, impairments in both muscle contraction and energy supply probably attenuate therapy outcome. In keeping with the above described physiological role of skeletal muscle carnosine and because muscle carnosine content may be lower in MS, **the primary aim of the present project is to investigate whether carnosine loading improves exercise therapy outcome (exercise capacity, body composition) and performance in MS.** If the latter hypothesis can be confirmed, muscle carnosine loading could be a novel intervention to improve exercise capacity and muscle function in this population.

Ergogenic potential of muscle carnosine loading and exercise therapy in MS

So far, it is clear that β -alanine intake enhances exercise capacity of untrained, trained and aged individuals by improving contractile properties, maintaining higher intracellular energy levels and optimizing training adaptations. Because early fatigue of contracting musculature during rehabilitation is the predominant cause of exercise cessation, postponing exercise-induced fatigue by β -alanine supplementation will be clinically very relevant (improving exercise therapy efficiency). Consequently, we aim to research the ergogenic potential of β -alanine intake in MS rehabilitation and **hypothesize that β -alanine supplementation in combination with exercise therapy optimizes therapy outcome (exercise capacity, body composition) and performance in this population.**

METHODS

Subjects

Twenty multiple sclerosis (MS) patients, diagnosed according to the McDonald criteria, and twenty healthy controls (HC), aged >18y will be included following written informed consent. Subjects will be excluded if they experience contraindications to participate in moderate to high intensity exercise, already participate in another study, experienced an acute MS exacerbation <6 months prior to the start of the study or have an EDSS score >3. This study will be performed in accordance with the Declaration of Helsinki and will be registered at ClinicalTrials.gov.

Study design

Following inclusion, baseline measurements (PRE) will be performed in MS patients (n=20) and HC (n=20). First, exercise capacity (maximal graded exercise test) will be evaluated. Prior to the maximal exercise test, heart function will be assessed by an experienced medical doctor, followed by measurement of whole body composition (DEXA). Furthermore, maximal strength of the back- and abdominal muscles will be assessed to evaluate core stability (important during prolonged cycle training). Hereafter, MS patients and HC will be randomly allocated to one of four intervention groups following 6 months of moderate-to-high-intensity cardiovascular exercise therapy with (MS β , n=10; HC β , n=10) or without (MS_{placebo}, n=10; HC_{placebo}, n=10) β -alanine supplementation. Groups not receiving β -alanine supplements, will receive placebo tablets that will be identical in taste and appearance. Following 6 months of exercise training (POST) measurements will be performed similar to baseline.

Exercise program

Moderate-to-high-intensity cardiovascular exercise therapy

All participants will perform a home-based supervised exercise training program. Participants will receive weekly training instructions using a smartphone based heart rate monitor app (Polar $^{\circledR}$). Training involves cycling, performed independently on their personal race bicycle. The exercise training program (6 months) involves 3 week cycles (week I-III). During week I, subjects will perform high volume moderate intensity cardiovascular cycle training (3x/week). Twice a week, subjects perform 3h training sessions (70-80% HR_{max}^{*}) and once a week a 1.5h session will be executed (80-90% HR_{max}). During week II, subjects will perform low volume maximum intensity interval cycle training (3/w). High intensity interval cycle training (HIIT) will consist of 3x maximal sprints (90-100% HR_{max}) of 1.5min, interspersed with 3min rest intervals. A 5min standardized warming up and 5min cooling down will be performed. Week III involves a recovery week where subjects will perform one training session of 1.5h at an exercise intensity of 70-80% HR_{max} and one session of HIIT. Throughout the intervention program at least 3 collective tours will be organized, where all subjects will perform a training session together, to improve group dynamics and motivation.

**obtained from the maximal graded exercise test*

β -alanine supplementation

The supplementation protocol of β -alanine (Etixx $^{\circledR}$ Omega Pharma Belgium NV) involves oral intake of 4 x 800mg (3.2g/day^{29, 43}) daily with at least 2h apart of slow-release β -alanine during the first 12 weeks. After this loading period, subjects will receive a maintenance dose of 2 x 800mg (1.6g/day) β -alanine for the remaining study duration. Placebo groups will follow the same supplementation protocol with placebo tablets that will have identical taste and appearance. All subjects will be advised to take the tablets together with meals. This supplement is frequently used to improve sport performances in athletes. The beta-alanine supplement consists of beta-alanine, hydroxymethylcellulose, cellulose, silicon dioxide, magnesium stearate and zinc. In some cases, taking beta-alanine can provoke a tingling feel (paresthesia) on the skin which is reversible within the hour. However, this is not dangerous and completely reversible. To prevent this paresthesia, β -alanine tablets will consist of slow-release β -alanine which, together with the spread intake throughout the day, will not provoke this discomfort.

Measurements

Exercise capacity & serum lactate. Exercise capacity will be assessed using a maximal (12-lead ECG) graded cardiopulmonary exercise test (♂: 30W+15W/min, ♀: 20W+10W/min) with pulmonary gas exchange analysis (Jaeger Oxycon®). Subjects will perform the exercise test on their personal bicycle (Cyclos2® Leipzig, Germany). VO₂, VE, RER will be monitored and 2min capillary blood samples will be obtained to analyse blood lactate concentrations (Analox®) and determine the anaerobic threshold before, during and after exercise. RER values will be evaluated to verify if the test was performed maximally (RER >1.1).

Body composition Whole body fat and lean tissue mass will be obtained using Dual Energy X-ray Absorptiometry scan (DEXA) (Hologic Series Delphi-A Fan Beam X-ray Bone Densitometer, Vilvoorde, Belgium). A calibrated analogue weight scale (Seca®) will be used to measure total body mass.

Statistical analysis

Baseline differences between groups and post-intervention differences will be analysed using an unpaired student's t-test and a 4x2 ANOVA for repeated measures, respectively (SAS Institute®). The threshold for statistical significance will be set at p<0.05.

Reference List

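### Training status may vary among entrants and affect response, but neither allocation nor analysis uses it; at 10 per arm this costs precision rather than causing bias

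*Combined protocol and SAP*

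**What the plan says.** The Exercise program section states "Training involves cycling, performed independently on their personal race bicycle". In week I of each three-week cycle, "Twice a week, subjects perform 3h training sessions", plus one session of 1.5 h; no run-in is described. Under Measurements, "Subjects will perform the exercise test on their personal bicycle".

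The Subjects section excludes people with contraindications to the exercise, those in another study, those with a recent exacerbation, and those with EDSS above 3. It has no criterion on cycling history or fitness.

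Under Study design, exercise capacity is measured first, and only then "MS patients and HC will be randomly allocated to one of four intervention groups", with 10 in each. No stratification factor, blocking or minimisation is named. The Statistical analysis section gives a 4x2 repeated-measures ANOVA and names no covariate.

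The Introduction, under Muscle carnosine loading, says that "trained muscles load more efficiently with carnosine than untrained muscles". Research objectives frames the aim for MS as a whole and says that, if the hypothesis is confirmed, "muscle carnosine loading could be a novel intervention to improve exercise capacity and muscle function in this population".

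**The concern.** The protocol names training status as something that affects how well the supplement loads, then uses it in neither eligibility, allocation nor analysis. The bicycle requirement and the long early rides favour people who already ride or are fit enough to start, but the criteria would also admit a novice who owns a suitable bicycle. A mix of the two is therefore possible.

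If regular cyclists and novices change by different amounts over six months of training, that difference goes into the error of the beta-alanine contrast. In a comparison of 10 with 10, one uneven split can move the estimate noticeably, and without a recorded training history nobody could tell afterwards whether it had. The PRE test could supply a proxy in time for allocation, but the plan does not use it there.

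A second, smaller matter is scope. The intended conclusion speaks of MS, whereas the people studied will have EDSS up to 3 and be able to train independently on a race bicycle.

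**Working it through.** The plan gives no power calculation, effect size or SD, so there is no figure of its own to reproduce beyond 4 × 10 = 40, which checks.

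**Inputs from the plan.** 20 MS patients, 10 per arm (Study design); significance threshold 0.05 (Statistical analysis; two-sided is assumed, since sidedness is not stated).

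**Inputs assumed.** K, the number of regular cyclists among the 20 MS patients: 4 to 16. Extra training gain of novices over cyclists: 5 to 15 percentage points, or b = 0 to 1.5 within-stratum SDs of change. True supplement effect for the power figures: 1.2 SD. The plan gives no SD of change, so the point scale and the SD scale cannot be linked.

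**1. Chance of imbalance.** Under simple 10:10 allocation the number of cyclists in one arm, x, is hypergeometric. For K = 10, P(x) = C(10,x)² / C(20,10), so

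P(7:3 or worse, either direction) = 2 × (1 + 100 + 2,025 + 14,400) / 184,756 = 33,052 / 184,756 = 0.179.

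The chance of a difference of four or more patients is 0.170 for K = 8 or 12, 0.141 for K = 6 or 14, and 0.087 for K = 4 or 16. At K = 10 about 9% falls in each direction. For a continuous training measure the standardised difference between arms has SD √(2/10) = 0.447; it exceeds 0.5 in 26% of allocations and 0.8 in 7%.

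**2. Shift in the contrast.** Shift = difference in proportion of cyclists × difference in gain. At 7:3 this is 0.4 × 5 = 2 points to 0.4 × 15 = 6 points. Over all allocations with K = 10, Var(x) = 10 × 0.5 × 0.5 × 10/19 = 1.316, so SD(x) = 1.147. The difference in proportions has SD 2 × 1.147/10 = 0.229, and the shift has SD 1.15 points (at 5) to 3.44 points (at 15), centred on zero.

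**3. Precision.** The effect detectable with 80% power at 10 v 10 is (1.960 + 0.842) × √(2/10) = 1.25 SD, or 1.32 SD by the t distribution. The unadjusted estimate has SD √(0.2 + (0.229b)²): 0.447 at b = 0 and 0.564 at b = 1.5. Simulation gives 0.45 and 0.57.

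**4. Simulation.** 8,000 trials per scenario, MS arms only, K = 10. The unadjusted test is the t-test on change (for two arms, the group-by-time test); the adjusted test adds the training factor.

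| | b = 0 | 0.5 | 1.0 | 1.5 |
|---|---|---|---|---|
| Simple, unadjusted: type I error | 0.054 | 0.049 | 0.050 | 0.053 |
| Simple, unadjusted: power | 0.71 | 0.69 | 0.60 | 0.51 |
| Simple, adjusted: power | 0.69 | 0.69 | 0.68 | 0.69 |
| Stratified, unadjusted: type I error | 0.047 | 0.041 | 0.026 | 0.013 |
| Stratified, unadjusted: power | 0.73 | 0.70 | 0.63 | 0.52 |
| Stratified, adjusted: power | 0.72 | 0.72 | 0.72 | 0.72 |

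The simulation error of each power figure is about √(0.7 × 0.3/8,000) = 0.005, so 0.71, 0.72 and 0.73 at b = 0 should not be read as different. The model takes training status to change the response to exercise, not the size of the supplement effect, and does not include the PRE value as a covariate. The planned 4x2 ANOVA also pools error with the healthy controls, so absolute power under it will differ.

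**The case against.** A reader might infer that the bicycle requirement means training status will vary widely. The documents do not support that: they give no data on entrants, and the same requirement could narrow entry to people who already cycle. Half of 20 is also the value of K that makes imbalance most likely.

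A reader might also infer that an imbalance in trained patients could imitate a beta-alanine effect because trained muscle loads better. It could not by that route. Better loading acts only in the arms that receive beta-alanine, and it produces nothing if loading has no effect. Imitation needs a further premise, that novices and cyclists respond differently to training itself. The Introduction makes this plausible by attributing part of the impairment in MS to inactivity, but it neither states the premise nor gives a size.

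Nor does the Introduction's gain of 13 to 30% in maximal power show modification by training status. It refers to untrained and aged subjects in efforts of 1 to 4 minutes, without a trained comparator. The section on ergogenic potential says beta-alanine helps untrained, trained and aged people alike.

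The top of the 5 to 15 point range is severe. The Introduction reports total training gains in MS of 10 to 15% and 25 to 30%, so a 15-point gap would be at least half of either.

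The PRE/POST analysis removes differences in baseline level. Chance imbalance is already allowed for in the 5% error rate. The absence of a named factor is silence about the method of randomisation, not a stated decision to leave training status out.

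All of this stands, and it limits the point to precision and interpretability. It does not remove it: differences in change survive a PRE/POST analysis, a comparison of this size has little precision to spare, and a usable proxy is already measured before allocation.

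**Conclusion.** The point holds as one about precision. The comparison is not biased, and type I error under the plan's simple allocation stayed at 0.049 to 0.054 in every scenario. The loss depends on how differently cyclists and novices respond: with half of the MS patients cyclists and a true effect of 1.2 SD, it is slight at 0.5 SD (power 0.71 to 0.69) and substantial at 1.0 and 1.5 SD (0.60 and 0.51). Adjustment recovers most of it, and stratification adds a little more.

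For a single result, sizeable imbalance in either direction has a chance of 9 to 18% over the values of K considered, and a 7:3 split would move the contrast by 2 to 6 points. These sizes rest on the assumed share of cyclists and the assumed difference in gain. What the documents themselves establish is that training status is unrestricted, is said to affect loading, and is unused in allocation and analysis.

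The wording of the conclusion should be narrowed whatever the size of these effects.

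**What to change.** - Before allocation, record regular cycling as yes or no against a fixed definition.
- Within MS and within healthy controls, stratify allocation on one two-level factor: that item, or PRE exercise capacity above or below a sex-specific cut set in advance. With 10 per arm, use no more than one factor. PRE capacity captures training history only in part, but it is already measured.
- Analyse POST with the PRE value and the stratification factor as covariates. Stratifying without adjusting is not enough: it makes the test conservative (type I error down to 0.013 at 1.5 SD) and leaves power at 0.52.
- Word the conclusion for MS patients with EDSS up to 3 who are able to train independently on a race bicycle.

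The cost is one screening question, a slightly more complex allocation list with small strata, one or two degrees of freedom, and a narrower stated population. If training status turns out to make no difference, adjustment without stratification loses a little power (0.71 to 0.69 in the simulation).

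### Optional: the change comparison inside the planned 4x2 ANOVA is valid, but prespecifying POST adjusted for PRE for β-alanine v placebo within MS would, on average, remove the effect of chance baseline imbalance, with a gain or small loss in precision that depends on unstated correlations and SDs

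*Combined protocol and SAP*

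**What the plan says.** The Statistical analysis section gives the whole plan in two sentences: "Baseline differences between groups and post-intervention differences will be analysed using an unpaired student's t-test and a 4x2 ANOVA for repeated measures, respectively", and "The threshold for statistical significance will be set at p<0.05". It names no baseline covariate, and it does not say which ANOVA term or contrast answers the question.

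Under Study design there are two measurement occasions. PRE is taken first; then "Hereafter, MS patients and HC will be randomly allocated to one of four intervention groups", with 10 people in each group (MS and healthy controls, each with β-alanine or placebo). The second occasion is at the end: "Following 6 months of exercise training (POST) measurements will be performed similar to baseline". PRE is therefore collected before allocation and can properly be used as a covariate.

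Under Research objectives, the "primary aim of the present project is to investigate whether carnosine loading improves exercise therapy outcome (exercise capacity, body composition) and performance in MS". The comparison that bears on this is β-alanine v placebo within MS, 10 v 10.

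The documents give no SD, PRE-POST correlation, target effect or power.

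**The concern.** In a two-occasion repeated-measures ANOVA, the group-by-time term is an analysis of POST minus PRE. (The group main effect is a different comparison.) Using changes fixes the slope of POST on PRE at 1. If the true slope is lower, the arm that happens to start higher tends to show a smaller change for reasons unrelated to treatment.

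Over all possible randomisations this averages out. In the one trial that is run it does not, and with 10 per arm sizeable chance imbalances are common. The plan tests for baseline differences but does not say what would follow from one. At stake are the dependence of the MS estimate on which arm started higher and, if ρ is moderate, some precision.

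**Working it through.** **Inputs from the documents:** n=10 per arm within MS; two occasions; significance threshold 0.05 (two-sided assumed, as no side is stated).

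**Assumptions:** ρ from 0.5 to 0.9; k = SD(POST)/SD(PRE), 1 unless stated; true effect 0.8 PRE SD for power; everyone completes; a single β-alanine v placebo contrast within MS. There is no planned figure to reproduce. PRE SD is set to 1.

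**1. Group-by-time equals a test on changes.** On one simulated four-group data set, the split-plot F for group-by-time and the one-way F on changes were both 3.7577, on 3 and 36 df.

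**2. Size of chance imbalance.** SD of d = √(2/10) = 0.447. P(|d|>0.5) = 2×[1-Φ(0.5/0.447)] = 0.264.

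**3. Shift.** Given d, the change-score estimate moves by -(1-ρk)d. At k=1 this is -0.50d, -0.30d, -0.20d and -0.10d at ρ=0.5, 0.7, 0.8 and 0.9. When |d|>0.5 the mean of |d| is about 0.725. A true effect of 0.8 SD is then estimated on average as 0.8 ∓ (1-ρ)×0.725:
- ρ=0.5: 0.44 or 1.16
- ρ=0.8: 0.66 or 0.94
- ρ=0.9: 0.73 or 0.87

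The lower value applies when the β-alanine arm starts higher. The estimate with an MS slope averages 0.80 in each case.

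**4. Variance.** Up to the common factor 2/n:
- change score: 1 + k² - 2ρk
- POST adjusted for PRE, slope estimated in MS: k²(1-ρ²)(1 + 1/16), where 1/16 = 1/(2n-4) is the average cost of estimating the slope

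At k=1 the ratio is ((1+ρ)/2)×1.0625, with variance break-even at ρ = 2/1.0625 - 1 = 0.88. Simulation agreed.

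| k | ρ=0.5 | ρ=0.7 | ρ=0.8 | ρ=0.9 |
|---|---|---|---|---|
| 0.9 | 0.71 | 0.80 | 0.84 | 0.86 |
| 1.0 | 0.80 | 0.90 | 0.96 | 1.01 |
| 1.1 | 0.87 | 0.98 | 1.03 | 1.06 |
| 1.2 | 0.93 | 1.03 | 1.06 | 1.04 |
| 1.3 | 0.97 | 1.05 | 1.06 | 0.98 |

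The average loss cannot exceed 1/16 = 6.25%. If only 8 per arm completed (assumed), the limit would be 1/12 = 8.3% and the k=1 break-even 0.85.

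**5. Power (noncentral t, effect 0.8 SD, k=1).** Example at ρ=0.5: the noncentrality for changes is 0.8/√(0.2×1) = 1.79; for the adjusted model it is 0.8/√(0.2×0.75×1.0625) = 2.00.

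| ρ | Change, pooled error, 36 df | Change, MS-only error, 18 df | MS slope, MS-only error, 17 df |
|---|---|---|---|
| 0.5 | 41% | 40% | 47% |
| 0.7 | 61% | 59% | 63% |
| 0.8 | 79% | 76% | 78% |
| 0.9 | 97% | 97% | 96% |

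The 36-df column requires equal error variance in MS and healthy controls. Against it, power break-even is near ρ=0.77.

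**6. Type I error.** Over all randomisations it is 5% for both methods with MS-only error. Given |d|>0.5, the change-score test rejects in about 9.6%, 7.8%, 6.6% and 6.0% at the four ρ values. In the other 74% of randomisations it rejects in about 3.4 to 4.7%. Check at ρ=0.5: 0.264×9.6 + 0.736×3.4 = 5.0%.

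**7. Slope and error choices.** One slope shared by all four groups costs 1/34 instead of 1/16, so the k=1 ratios become 0.77, 0.88, 0.93 and 0.98 if the slopes are equal. If they are not (MS ρ=0.9, healthy controls 0.5), the ratio is 1.23 and a shift of +0.20d appears. Pooling the error across MS and healthy controls gives the MS change contrast a type I error of 12.7% at MS 0.5/controls 0.9, and 0.7% at MS 0.9/controls 0.7.

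**The case against.** The strongest objection is that nothing here is wrong with the plan. The change comparison is unbiased over randomisations and holds its 5% level, given equal error variances or MS-only error. A reader might infer from the conditional rates of 6 to 9.6% that the test is invalid. The documents do not support that: those rates describe the least balanced quarter of randomisations and are offset in the rest. This objection stands and sets the grade.

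A second objection is that every size depends on ρ and k, which the documents do not give, and that the gain changes sign within a plausible range. This also stands. Adults of both sexes are likely to differ widely from one another, which would tend to raise ρ. The Introduction cites gains of 25-30% after high-intensity training; if gains were proportional to baseline (an assumption), k would be about 1.25 to 1.3, where there is little gain and often a small loss. A saving of 20% should not be read as the expected result.

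Third, the cost is not one degree of freedom. Going from 18 to 17 compares two MS-only analyses; against the planned pooled ANOVA it is 36 to 17. This stands and is reflected in the power table.

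Fourth, a reader might take the Introduction's remark that exercise "effects are lower compared to healthy controls and some other disease populations" as evidence of a different PRE slope in MS. It concerns mean effects, which a disease term absorbs, and says nothing about slopes. The documents support neither equal nor unequal slopes.

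Finally, the estimated slope is itself noisy. At k=1 its SE is about √((1-ρ²)/16), or 0.15 at ρ=0.8 and 0.11 at ρ=0.9, against errors of 0.20 and 0.10 from fixing the slope at 1. The shift is removed on average, not exactly in a given trial.

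**Conclusion.** The point holds as an optional improvement. The planned group-by-time comparison is valid; adjusting for a PRE value already collected would make the MS estimate independent, on average, of which arm started higher. That requires a linear PRE-POST relation with one slope in both MS arms.

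The effect on precision is modest and uncertain: about a 20% lower variance at ρ=0.5 and k=1, nothing near ρ=0.88, and an average loss of up to about 6% when POST SD exceeds PRE SD by 10-30% at high ρ. Against the planned pooled ANOVA with equal error variances, power rises by about 6 points at ρ=0.5 and falls by about 1 point at 0.8 and 0.9. All these sizes rest on assumed ρ, k and effect, full completion, and a within-MS contrast that the plan does not name.

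**What to change.** In the Statistical analysis section, name the β-alanine v placebo contrast within MS and analyse POST adjusted for PRE of the same outcome. State that the adjustment applies whatever the baseline t-tests show. Keep MS v healthy controls as a comparison of unadjusted changes, because those groups are not randomised.

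A cautious form is a linear model with PRE, supplement, disease, supplement-by-disease and PRE-by-disease, with residual variance estimated separately in MS and healthy controls. For the MS contrast this equals regressing POST on PRE and supplement in the 20 MS patients. A common slope is cheaper but relies on an equality that the documents do not support. Whichever is chosen should be fixed before outcome data are seen.

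The cost is SAP wording, a separate analysis for MS v healthy controls, the error degrees of freedom described above (17 in place of 36 for the cautious form), and the possible small loss of precision. No new data are needed.
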